#### 2.3.1. Screening Procedures

The outpatient visits will take place in various outpatient clinics and/or procedural areas throughout the University of Pittsburgh Medical Center (UPMC) Presbyterian and UPMC Montefiore Hospitals. The screening procedures will take place over 2 days if screening RHC is needed. Subjects will be asked to fast a minimum of 8 hours prior to each visit. These screening procedures will determine eligibility for the study.

- Obtain written informed consent
- Complete history and physical examination to include body weight, height
- Vital signs that include: blood pressure (BP), pulse, respirations, and pulse oximetry
- Obtain waist measurement
- Review of concomitant medications
- NYHA functional class assessment
- 6 minute walk test (6MWT) and Borg scale
- MetHb level via co-oximetry (pre single dose and 30 minutes post single dose). Due
  to unknown reasons the co-oximeter device may not be able to read metHb levels. In
  that event, a blood sample will be collected to test metHb levels at approximately 3045 minutes after the 40mg dose.
- Blood samples: fasting glucose, comprehensive metabolic panel, hemoglobin A1C, fasting lipid profile, PT/PTT, complete blood count, platelet and differential, NT-proBNP. The total volume of blood drawn is approximately 1 ½ tablespoons (20 mL). If any of the above tests were done within 30 days before the screening visit, they may or may not be repeated for research purposes.
- Urine pregnancy test for women of childbearing potential
- Echocardiogram (if subject has had an echocardiogram within the past year we may not obtain during screening)
- Right heart catheterization (with optional micromanometry), research blood samples
  for plasma nitrite concentrations, red cell iron-nitrosyl-hemoglobin and platelet studies,
  and open label 40mg oral nitrite dosing with methemoglobin level. Research blood
  samples will be collected prior to taking the 40mg oral nitrite and approximately
  30-45 minutes post-dose.
- A RHC may be performed to determine the PH-HFpEF eligibility criteria. The RHC will be conducted at UPMC Presbyterian Hospital, 3rd FL Catheterization Laboratory. The RHC hemodynamic measurement parameters for PH-HFpEF eligibility are as follows: mPAP ≥ 25 mm Hg; PCWP ≥15 and TPG ≥ 12. If a RHC has been completed within 12 months from enrollment, test results may be considered for baseline measurements. The total volume of blood drawn is approximately 1 ¾ tablespoons

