#### Nitrite:

Sodium nitrite has been used commercially as a food preservative, an anti-corrosive agent, a coloring agent, and an anti-anginal agent, with additional uses in laxatives, burn ointments, and liniments. Amyl nitrite has been inhaled or ingested as an euphoric stimulant. Nitrite has also been found as a contaminant in well water. Literature searches generated case reports of nausea, vomiting, abdominal pain, dizziness, headache, flushing, cyanosis, tachypnea, dyspnea, hypotension, and death attributed to excess nitrite (high-dose) exposure from these sources as a consequence of methemoglobinemia due to oxidation of heme-iron in oxyhemoglobin. Normal background methemoglobin production is 1-3%. If levels of methemoglobin rise above approximately 30% of total hemoglobin, a subject may appear cyanotic and experience dyspnea, due to the reduced oxygen carrying capacity of hemoglobin

(methemoglobin cannot bind oxygen). Levels above 50% can cause seizures, hypotension, coma, and death. Sodium nitrite administration for cyanide poisoning at the labeled dosage of 300 mg causes methemoglobinemia, a desirable effect, as methemoglobin binds to cyanide, thus protecting cellular mitochondria. A standard dose of nitrite used for cyanide poisoning is 300 mg up to 600 mg. Note that methemoglobin levels have never risen higher than 3% at the currently used therapeutic doses (< 75 mg) in 80 volunteers in phase I studies at the NIH.

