The Sponsor of this study proposal, [name], has previously held an IND for sodium nitrite (IND # 70,411) for cardiovascular applications and currently has an approved IND for the use of sodium nitrite for lung transplant recipients (IND # 111,643). The cardiovascular IND involved the administration of sodium nitrite to 69 normal volunteers in 4 phase I-II clinical trials without observed adverse effects. He has also treated 11 subjects with sickle cell disease on this IND without observed adverse effects. The lower doses of nitrite used in these investigational treatment regimens – 60-120 mg daily or 20-40% of the dose (300mg) used in the emergency treatment of cyanide poisoning – do not produce methemoglobin levels greater than 3% and have not been associated with clinically significant hypotension. There have been no adverse events noted in the 80 treated normal human volunteers and patients with sickle cell disease. In another study by [name] et al., 18 healthy adults received an infusion of sodium nitrite totaling 75 mg (15 minutes each x 2 infusions). This was associated with a 7 mmHg decrease in mean arterial pressure, a peak methemoglobin of less 3%, and no other significant effects. Note this single dose is 1.9 times the single dose per time of day we plan to use in this trial.

In an open-label three-way crossover study, 9 healthy adult subjects received two single high dose oral sodium nitrite aqueous solutions (0.12 and 0.06 mmol NaNo2/mmol Hb, equivalent to 290-380 mg and 140-190 mg sodium nitrite, respectively, depending on the total body hemoglobin level of the person) and one intravenous sodium nitrite dose (0.12 mmol NaNo2/mmol Hb). Note that this is 1.2-3.2 times the daily dose we plan to use in this trial. There was a washout period of at least 7 days between each of the treatments. Mild headache occurred in 44-55% of subjects and was the most frequent complaint during each treatment session, which the authors ascribed to the sodium nitrite, not methemoglobinemia, as the percentage of methemoglobinemia stayed below clinically toxic levels (<15%). By report, up to 22% experienced nausea, which subsided within half an hour. The pharmacokinetic analysis of this study indicated similar bioavailability of oral and IV delivery of nitrite, as well as similar side effect and safety profiles.

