## Hematologic

Common: noneFrequent: none

Rare: methemoglobinemia

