## Stopping Rule

For safety reasons, we propose to temporarily suspend enrollment and review with our DSMB if any two subjects experience the following despite dose reduction:

A single occurrence of venous methemoglobin level >5%
 If subjects report change in skin tone and dizziness or other signs of methemoglobinemia for ≥24 hours, an interim visit will be scheduled (if not already being seen for a research visit) and the following steps will occur. The visit can be conducted in UPMC Presbyterian or the TRC.

The physician investigator will factor relevant subject symptoms and hemodynamics and:

- Determine if unblinding is needed (if methemoglobin % >5) and,
- If subject is willing to do an interim visit with repeat drug dosing of 20 mg with follow up methemoglobin and BP pressure monitoring or
- Subject should be withdrawn

Interim visit: If methemoglobin is greater than 5%, the PI will be unblinded to drug or placebo assignment. If subjects are on nitrite, subjects will be asked to repeat drug dosing of 20 mg sodium nitrite with follow up methemoglobin and hemodynamic monitoring. A study physician or PI will evaluate data and make a determination regarding discharge on 20 mg tid. If discharged on 20 mg tid, subjects will be contacted via phone for the next 2 days for symptom re-assessment. If symptoms remain resolved, subjects will continue on 20 mg tid. If symptoms persist, subjects will be requested to come in for repeat

methemoglobin testing after 3 days. If level persists above 5% on lower dose, participation in the study for the subject will be discontinued.

- Blood pressure (BP) and related symptoms: If subjects experience lightheadedness or dizziness, we request that they call the study coordinator who will assess their symptoms, compare to baseline levels, and discuss need for interim visit with study physician. If a visit is indicated, BP, RR, heart rate, pulse co-oximetry and methemoglobin level via co-oximetry will be measured.
  - If systolic BP ≤ 90mm Hg, the study drug will be reduced from 40 TID to 20 TID. Subjects will be reassessed via telephone to ensure that the patient is stable on the new dose. If stable and asymptomatic, subjects will continue with the half dose.

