  - If subjects are symptomatic with dizziness, lightheadedness for ≥ 24 hours, and require fluid replacement or other therapy for hypotension, subjects will be requested to return to clinic for an interim visit for assessment of vitals, methemoglobin percent, and evaluation by an investigator-physician to reevaluate the subject's suitability for continued participation based on symptoms.
  - If SBP remains ≤ 90mm Hg and symptomatic and at the lowest dosage of 20mg TID, subject will be withdrawn.

If an unexpected fatal event or any of the above life-threatening events occur despite dose reduction, the study will be halted, until data review by investigators and the Data Safety Monitoring Board has rendered a final recommendation about study continuation.

Other potential reasons for stopping participation in study activities

- 1. Subject participation will be discontinued if a participant has a positive pregnancy test at any point during study participation.
- 2. In the event that the medication compliance rate is < 80%, subjects will be reeducated on medication compliance. If medication compliance falls outside of the acceptable range more than 2 times, the study investigators will discuss subject eligibility for continued participation in the study.

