## 5.5.3 Parameters to be Monitored

The following progress will be monitored throughout the course of the research to ensure the safety of subjects as well as the integrity and confidentiality of their data.

- An evaluation of the progress of the research study, including subject recruitment and retention, and an assessment of the timeliness and quality of the data.
- A review of collected data (including adverse events, unanticipated problems, and subject withdrawals) to determine whether there is a change to the anticipated benefit-to-risk assessment of study participation and whether the study should continue as originally designed, should be changed, or should be terminated.
- An assessment of external factors or relevant information (eg. pertinent scientific literature reports or therapeutic development, results of related studies) that may have an impact on the safety and study participants or the ethics of the research study.

• A review of study procedures designed to protect the privacy of the research subjects and the confidentiality of their research data.

The severity of adverse changes in physical signs or symptoms will be classified as follows:

- Grade 1 (Mild): asymptomatic or mild symptoms; clinical or diagnostic observation only; intervention not indicated.
- Grade 2 (Moderate): minimal, local, or noninvasive intervention indicated; limiting ageappropriate ADL (Activities of Daily Living).
- Grade 3 (Severe): medically significant but not immediately life-threatening; hospitalization or prolongation of hospitalization indicated; disabling; limiting self-care ADL.
- Grade 4 (Life-threatening): consequences; urgent intervention indicated.
- Grade 5 (Death): event is a direct cause of death.

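### As worded, the stopping rule in 5.5.2 triggers no automatic pause or halt for a life-threatening methemoglobin or hypotension event on the tested 40 mg dose

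*Combined protocol and SAP*

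**What the plan says.** The Stopping Rule in 5.5.2 acts on the whole trial in two ways.

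- Enrolment pause: "we propose to temporarily suspend enrollment and review with our DSMB if any two subjects experience the following despite dose reduction". The events listed below it are a venous methemoglobin above 5%, and low blood pressure with related symptoms.
- Study halt: "If an unexpected fatal event or any of the above life-threatening events occur despite dose reduction, the study will be halted". The halt lasts until the investigators and the DSMB have reviewed the data and a final recommendation has been made.

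The rest of the rule manages the individual subject. Methemoglobin above 5% leads to unblinding of the principal investigator and, if the subject is on nitrite, a repeat dose at 20 mg. Systolic pressure of 90 mmHg or less leads to a step-down from 40 to 20 mg three times daily. If the problem persists on 20 mg, the subject leaves treatment: for blood pressure, "If SBP remains ≤ 90mm Hg and symptomatic and at the lowest dosage of 20mg TID, subject will be withdrawn".

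The dose under test is 40 mg three times daily (2.2.1). Section 2.3.1 also includes "open label 40mg oral nitrite dosing with methemoglobin level" with the screening right heart catheterization, where one is done. The Randomization part of 2.3.2 has the first blinded dose taken under supervision.

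Severity is graded in the following subsection, 5.5.3: "Grade 4 (Life-threatening): consequences; urgent intervention indicated". The Stopping Rule does not refer to it.

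**The concern.** A stopping rule fixes in advance what happens after a serious event, so that the response does not depend on judgement at the time. Here both trial-level responses apply only once the dose has been lowered. All subjects are assigned 40 mg or matching placebo, and only those who run into trouble are stepped down. The condition therefore removes from the rule the dose that most nitrite-treated subjects will be taking.

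After a life-threatening methemoglobin or hypotension event on 40 mg, other subjects could go on being enrolled and dosed unless the investigator or the DSMB chose to intervene. The wording probably does not reflect the intent, but it is what a site would have to follow.

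**Working it through.** The protocol states no operating characteristic for this rule, so there is no figure to reproduce. The check is a reading of the rule against each situation in which an event could occur.

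| Situation | Two-subject pause | Study halt | What the text provides |
|---|---|---|---|
| Life-threatening event at the open-label 40 mg screening dose (2.3.1) | No: no reduction can have happened | No, same reason | Individual care, reporting, discretionary review |
| Same, at the first supervised dose (2.3.2, Randomization) | No | No | As above |
| Same, later on 40 mg before any step-down | No | No | As above, with step-down or withdrawal |
| Methemoglobin above 5%, or persistent symptomatic low pressure, on 20 mg, not life-threatening | Counts towards two | Not on the natural reading | Withdrawal of the subject if it persists |
| Life-threatening event of a listed type on 20 mg | Counts | Yes | Automatic halt |

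**Other routes to stopping.** Section 5.5.1 gives the DSMB interim monitoring for safety. Sections 5.5.3 and 5.5.4 call for review of whether the study should continue, and the DSMB meets as needed and at least every six months. Section 5.6.2 mentions continuous DSMB monitoring. Section 2.7 allows a subject to be withdrawn. Section 5.5.6 requires 24-hour reporting to the DSMB and IRB of unexpected fatal or life-threatening events associated with the drug or procedures, and FDA notice within 7 days. All of these are discretionary, concern one subject, or are reporting duties. None makes a pause or halt automatic. The 24-hour duty is limited to unexpected events, a term the protocol does not define. Section 5.1 lists the relevant events among the anticipated risks (for example "Rare: methemoglobinemia", with hypotension, seizure and coma under other headings), so it is not certain that this duty would cover them.

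**What counts as life-threatening.** The listed thresholds are not themselves at that level. Section 5.1 places cyanosis and dyspnea at about 30% methemoglobin, and says "Levels above 50% can cause seizures, hypotension, coma, and death". The 5% trigger is 5/30 = one sixth of the first level and 5/50 = one tenth of the second. The sensible reading is therefore an event of a listed type that reaches Grade 4.

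**How often.** Section 5.1 reports: "There have been no adverse events noted in the 80 treated normal human volunteers and patients with sickle cell disease". From 0 of 80, the exact one-sided 95% upper bound is 1 − 0.05^(1/80) = 3.7% per subject. With per-subject probability p, the chance of at least one event in 26 subjects is 1 − (1 − p)^26, and the expected number is 26p:

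- p = 0.1% (assumed): 2.6%; 0.03 expected.
- p = 1% (assumed): 23%; 0.26 expected.
- p = 3.7% (the bound): 62%; 0.96 expected, and about a 25% chance of two or more.

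For events on unreduced 40 mg, the chance of an automatic halt under the literal rule is 0 whatever p is. The figures above are illustrations. The 80 subjects were healthy volunteers and sickle cell patients, so the bound does not carry over to PH-HFpEF. It also says nothing about background or placebo-period hypotension.

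**The case against.** The strongest reply is that the DSMB would act anyway. It is independent, can meet at any time, and is charged with protecting subjects. This stands as far as it goes. A reader might infer from the rule that nothing would stop the trial after a life-threatening event on 40 mg. The documents do not support that: what is missing is the automatic trigger, and a discretionary route remains.

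A reader might also infer that the halt has no usable trigger apart from a death, or that it makes the two-subject pause redundant, because no listed event is called life-threatening. That goes too far. Reading the halt as a listed type of event that reaches Grade 4 gives a coherent ladder: two lesser events on 20 mg pause enrolment, and one life-threatening event halts the study. What remains is a missing cross-reference.

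The reply can also point to the low likelihood. Section 5.1 reports methemoglobin below 15% after single oral doses of 140 to 380 mg, which is 3.5 to 9.5 times a 40 mg dose. It also reports only asymptomatic toxicity in a prolonged infusion study at a dose the protocol puts at 8.2 times the daily dose. Systolic pressure below 110 mmHg is an exclusion (3.3). These points make the scenario unlikely, particularly for methemoglobin. They come from other populations and do not correct the wording.

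Continuing the trial after a non-serious event on 40 mg that resolves on 20 mg is a reasonable design choice and is not disputed.

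**Conclusion.** The point holds as a minor drafting defect in a safety rule. Followed as written, section 5.5.2 gives no automatic trial-level action for a life-threatening methemoglobin or hypotension event on 40 mg, including at the screening and first supervised doses. This follows from the text and needs no assumed event rate. The missing link to Grade 4 is secondary.

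Two further inferences are not supported. First, it is unclear whether the dose-reduction condition also governs an unexpected death, and the point does not rest on that. Second, the 0.96 expected events at the 0 of 80 bound should not be read as a ceiling of about one extra halt. It is an expected count, and it comes from a different population. Such events should be rare, but the documents give no rate in PH-HFpEF from which to bound them. The primary endpoint and the analysis are unaffected.

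**What to change.** Replace the halt sentence in 5.5.2 with wording such as:

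> The study stops, pending data review by the investigators and a final DSMB recommendation, if either of these occurs at any dose, with or without an earlier dose reduction: (i) an unexpected fatal event; (ii) Grade 4 (section 5.5.3) methemoglobinemia or hypotension judged at least possibly related to study drug.

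Keep the two-subject enrolment pause, with one added line saying that it applies to non-life-threatening events on 20 mg three times daily.

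This needs no new visits, tests or subjects. The cost is an occasional extra temporary halt and DSMB review, possibly for an event later judged unrelated. The relatedness condition in (ii) limits halts for background hypotension in this population, at the price of a causality judgement when the event occurs.

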## 5.5.3 Parameters to be Monitored

The following progress will be monitored throughout the course of the research to ensure the safety of subjects as well as the integrity and confidentiality of their data.

- An evaluation of the progress of the research study, including subject recruitment and retention, and an assessment of the timeliness and quality of the data.
- A review of collected data (including adverse events, unanticipated problems, and subject withdrawals) to determine whether there is a change to the anticipated benefit-to-risk assessment of study participation and whether the study should continue as originally designed, should be changed, or should be terminated.
- An assessment of external factors or relevant information (eg. pertinent scientific literature reports or therapeutic development, results of related studies) that may have an impact on the safety and study participants or the ethics of the research study.

• A review of study procedures designed to protect the privacy of the research subjects and the confidentiality of their research data.

The severity of adverse changes in physical signs or symptoms will be classified as follows:

- Grade 1 (Mild): asymptomatic or mild symptoms; clinical or diagnostic observation only; intervention not indicated.
- Grade 2 (Moderate): minimal, local, or noninvasive intervention indicated; limiting ageappropriate ADL (Activities of Daily Living).
- Grade 3 (Severe): medically significant but not immediately life-threatening; hospitalization or prolongation of hospitalization indicated; disabling; limiting self-care ADL.
- Grade 4 (Life-threatening): consequences; urgent intervention indicated.
- Grade 5 (Death): event is a direct cause of death.

## 5.5.4 Frequency of Monitoring

The Investigator will review subject safety data as it is generated. The Investigator and the research staff will meet at approximately monthly intervals to re-evaluate study goals, subject recruitment, data coding and retention, documentation and identification of adverse events, complaints, and confidentiality of subjects. There will be an evaluation of the progress of the research study, including assessments of data quality, time lines, participant recruitment, accrual, and retention. The Investigator will also review the outcome and adverse event data to determine whether there is any change to the anticipated benefit-to-risk ratio of study participation and whether the study should continue as originally designed or should be reevaluated and changed.

The DSMB will also be expected to meet as needed, but not less than every six months to provide an overall summary status report to the regulatory agencies.

# 5.5.5 Reportable Adverse Events

For this study, a serious adverse event is any untoward clinical event that is thought by the investigator to be study-related, that is also:

- 1. Fatal or immediately life threatening
- 2. Permanently disabling, or severely incapacitating
- 3. Requires or prolongs inpatient hospitalization
- 4. Important medical events that may not result in death, be life threatening, or require hospitalization may be considered serious adverse events when, based upon appropriate medical judgment, they may jeopardize the patient, or subject, and may require medical or surgical intervention to prevent one of the serious outcomes listed above.

If clinically important and unexpected adverse experiences, or clinically important studyrelated adverse experiences occur, they will be recorded on the adverse event case report form.

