#### 2.3.3. Treatment Period and Monitoring

The follow up visits will take place in various outpatient clinics and/or procedural areas throughout the University of Pittsburgh Medical Center (UPMC) Presbyterian Hospital, UPMC Montefiore Hospital, Kaufmann Building, and/or Falk Clinic. The intravenous glucose tolerance test (IVGTT) will be performed at the Montefiore Clinical and Translational Research Center (CTRC).

Phone Visits: Weeks 4 and 8 (+/- 7 Days) following the start of each treatment arm

- Interval history (ER visits/hospitalizations)
- · Review of concomitant medications
- Review for compliance and symptoms
- AE/SAE assessment

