#### 2.7.1. Dropouts and withdrawals

To be considered complete, a subject must complete all study visits as specified in the protocol without violations of the protocol so significant as to obscure the response to study treatment.

Subjects who fail to complete all study required visits will not be considered complete and may not enroll at a later date and will not be replaced. A record will be kept of all subjects who fail to complete all study visits and their primary reasons for discontinuation.

In the event of subject withdrawal, subjects will be encouraged to continue all follow-up visits for safety monitoring or to continue follow up as directed by their personal primary physicians, unless the subject withdraws consent at any time (without having to justify the decision). All available data from subjects who discontinued during the study, for whatever reason, will be included in the safety analysis.

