## 5.5.2 Data Safety Monitoring Plan

Assuring patient safety is an essential component of this protocol. The study Principal Investigator has primary responsibility for the oversight of the data and safety monitoring. The study investigators will evaluate all adverse events. All subjects who have AEs, whether considered associated with the use of the study medication or not, must be monitored to determine the outcome. The clinical course of the AE will be followed up according to accepted standards of medical practice, even after the end of the period of observation, until a satisfactory explanation is found or the Principal Investigator considers it medically justifiable to terminate follow-up.

All untoward medical occurrences observed in subjects receiving the study drug will be recorded on the participants' adverse event worksheets by the study coordinator under the supervision of the principal investigator. The worksheets will then be reviewed for completeness and internal consistency. In addition to internal safeguards built into a computerized system, external safeguards will be put in place to ensure that access to the computerized system and to the data is restricted to authorized personnel. Training conducted by qualified individuals on a continuing basis will be provided to individuals in the specific

operations with regard to computerized systems that they are to utilitze during the course of the study.

The Sponsor and Investigator will prepare a detailed written summary of serious, unexpected, and treatment-related adverse events, and will compare and contrast each event with prior events. The written summary will be provided to the DSMB and the IRB.

In addition, the DSMB Report addressing the following information will be submitted to the IRB at the time of continuing review, annually or more often as required:

- A list of the research personnel who participated in the data and safety monitoring.
- The frequency of monitoring that took place during the renewal intervals and/or the dates that data and safety monitoring was conducted.
- A summary of cumulative data related to unanticipated problems (including adverse events) including a determination of causality and whether the risk to benefit assessment has changed.
- If appropriate, a summary of pertinent scientific literature reports, therapeutic developments, or results of related studies that may have an impact on the safety of study participants or the ethics of the research study.

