## **5.5.6 Adverse Events Reporting Timeline**

Life-threatening or fatal unexpected adverse events associated with the use of the study drug

or procedures must be reported to the DSMB and the IRB within 24 hours of discovery of the incident with subsequent follow-up submission of a detailed written report.

The FDA must be notified by telephone or facsimile transmission of a human adverse event that is fatal or life-threatening no later than 7 calendar days after receiving the respective human adverse event information, followed by the subsequent submission of a written IND Safety Report.

Serious and unexpected adverse events associated with the use of the study drug or procedures must be reported to the DSMB and the IRB with subsequent follow-up submission of a detailed written report in accordance with the respective policies and procedures of the IRB. Written IND Safety Reports will be submitted to the FDA as soon as possible and, in no event, later than 15 calendar days following the investigator-sponsor's receipt of the respective adverse event information.

A summary report of the DSMB's findings will be prepared and submitted to the regulatory agencies.

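### Section 5.5.5 makes the investigator's opinion of relatedness part of the SAE definition, so a death or hospitalisation judged unrelated is not an SAE

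*Combined protocol and SAP*

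**What the plan says.** Section 5.5.5 (Reportable Adverse Events) contains the only definition of a serious adverse event: "a serious adverse event is any untoward clinical event that is thought by the investigator to be study-related, that is also" one of four things, namely fatal or immediately life-threatening, permanently disabling or severely incapacitating, a cause of new or prolonged inpatient stay, or an important medical event. The same section then says which events go on the case report form. They are clinically important events that are either unexpected or study-related, and "they will be recorded on the adverse event case report form".

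Section 5.5.2 (Data Safety Monitoring Plan) is broader. "All untoward medical occurrences observed in subjects receiving the study drug will be recorded" on worksheets, and "All subjects who have AEs, whether considered associated with the use of the study medication or not, must be monitored to determine the outcome". For the DSMB and IRB it asks for a "detailed written summary of serious, unexpected, and treatment-related adverse events".

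Section 5.5.6 adds a relatedness condition of its own: "Serious and unexpected adverse events associated with the use of the study drug or procedures must be reported to the DSMB and the IRB".

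The label is also used in data collection. "AE/SAE assessment" is listed in section 2.3.3 for the phone visits at weeks 4 and 8, any clinic visit held in their place, week 10 and end of treatment, and the cross-over visit. Section 2.7.1 says that data from subjects who discontinue "will be included in the safety analysis". No section specifies an SAE table.

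**The concern.** Seriousness describes the outcome of an event. Relatedness is a judgement about its cause. Section 5.5.5 merges the two, so a subject can die or be admitted to hospital during a treatment period and contribute nothing to the SAE count, because the investigator thought the cause lay elsewhere.

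A randomised, placebo-controlled comparison is useful for safety because it does not need a causal verdict on each event: the two treatments can be compared on all serious outcomes. Under this definition an SAE comparison would hold attributed events only. A reader would take a low SAE count to mean few deaths or hospitalisations, when it would mean few that were judged study-related.

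The effect is limited to safety reporting. The primary comparison of exercise mPAP and the stated stopping triggers do not depend on the SAE label.

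**Working it through.** **The definition applied**

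The words joining the two parts of the 5.5.5 sentence make both conditions necessary.

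| Outcome | Investigator's view | Status under 5.5.5 |
|---|---|---|
| Death or hospitalisation | Study-related | SAE |
| Death or hospitalisation | Not study-related | AE only |

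**Does any other section restore SAE status?**

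- 5.5.2 keeps the event on the worksheet and requires follow-up, but as an adverse event.
- 5.5.3 grades severity, with hospitalisation in Grade 3 and death in Grade 5. It does not mention seriousness.
- 5.5.6 requires FDA notification of a fatal or life-threatening event within 7 calendar days, and that sentence has no attribution test. It governs notification, not classification.
- The Stopping Rule in 5.5.2 halts the study for an unexpected fatal event, also without an attribution test. It does not define an SAE.

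None of these returns the event to the SAE count.

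**Is the clause needed for reporting?**

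No. The written summary in 5.5.2 and the DSMB/IRB rule in 5.5.6 each list relatedness as a further condition beside seriousness. If relatedness were already part of seriousness, those conditions would be redundant. The two sections treat the concepts as separate and 5.5.5 does not. For these reports the clause adds nothing; its distinct effect is on classification.

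**The case report form rule**

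An expected, unrelated hospitalisation meets neither limb of the 5.5.5 rule (unexpected, or study-related), yet 5.5.2 requires it on a worksheet. The two rules do not match.

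**Illustrative size**

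The documents give no rate of deaths, hospitalisations or unrelated events, so the number that would be reclassified cannot be calculated. As an assumption, let k of the planned n = 26 subjects be hospitalised, with k from 1 to 6, and all be judged unrelated. The SAE count is then 0/26. Exact (Clopper-Pearson) two-sided 95% limits are:

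- lower = Beta quantile(0.025; k, n − k + 1)
- upper = Beta quantile(0.975; k + 1, n − k)

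For k = 0 the upper limit reduces to 1 − 0.025^(1/26) = 13.2%.

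| k | k/26 | 95% limits |
|---|---|---|
| 0 (SAE count under 5.5.5) | 0.0% | 0 to 13.2% |
| 1 | 3.8% | 0.1 to 19.6% |
| 2 | 7.7% | 0.9 to 25.1% |
| 3 | 11.5% | 2.4 to 30.2% |
| 4 | 15.4% | 4.4 to 34.9% |
| 5 | 19.2% | 6.6 to 39.4% |
| 6 | 23.1% | 9.0 to 43.6% |

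Since 3/26 = 11.5% is below 13.2% and 4/26 = 15.4% is above it, from four hospitalised subjects upward the observed outcome-based rate exceeds the upper limit that the 0/26 count would imply. At the other extreme, if every event is judged related, the two counts are the same.

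**The case against.** The strongest reply is that this is a labelling defect with little practical effect.

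- **The events are collected anyway.** Interval history in 2.3.3 asks directly about emergency visits and hospitalisations, without regard to cause, and Table 1 schedules it throughout follow-up. With the worksheets and severity grades, a count of deaths and hospitalisations by period could be rebuilt. This stands, and it limits the harm. It does not change what is called an SAE.
- **Causality is partly separate already.** The DSMB report in 5.5.2 includes a determination of causality. True, but for that report; it does not remove attribution from the definition.
- **No SAE table is planned.** Section 2.8 promises none, and Table 1 lists only AE assessment. So an SAE count is an inference. It is a fair one: 2.7.1 names a safety analysis, 2.3.3 uses the SAE term, and any SAE count made under this protocol would inherit the definition.
- **Blinding protects the comparison.** In a double-blind trial attribution should be largely even across treatments. This holds, apart from the unblinding of the principal investigator that the Stopping Rule provides for when methemoglobin exceeds 5%. Even attribution would still understate the total.
- **The case report form rule does not say only.** Correct. It is a mismatch to reconcile rather than a flat contradiction.
- **The numerical range is assumed and shows the extreme case.** Also correct. It describes one pooled count and says nothing about a difference between nitrite and placebo.

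**Conclusion.** The concern holds. As written, a death or hospitalisation that the investigator thinks unrelated is not an SAE, and no other section makes it one. The definition is also out of step with 5.5.2 and 5.5.6, which treat relatedness as a condition separate from seriousness.

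The size depends on an event rate and an attribution pattern that the documents do not give. On the assumed range of 1 to 6 hospitalised subjects out of 26, the SAE count could be 0/26 when the outcome-based rate is anywhere from 3.8% to 23.1%; with full attribution there is no difference. The events themselves are not lost, an all-AE comparison remains possible, and neither the primary inference nor the stopping triggers are affected. It should be fixed, because any SAE result would otherwise be open to misreading.

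**What to change.** 1. In 5.5.5, delete the clause requiring the investigator to think the event study-related, so that seriousness is defined by outcome alone.
2. Record causality as a separate field for every adverse event.
3. Align the case report form rule in 5.5.5 with 5.5.2, so that all adverse events in both treatment periods are entered.
4. Keep relatedness and expectedness as criteria for expedited reporting in 5.5.6, where they already appear.
5. Tabulate all SAEs by treatment (nitrite, placebo), with study-related SAEs as a subset. Showing the 2-week washout and the 6-month open-label period separately would be a useful addition, but the correction does not depend on it.

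The cost is a wording amendment and slightly more data entry, since hospitalisations are already asked about at interval history. The reported SAE count may be higher. No dose, stopping trigger or other clinical rule changes.
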